When the first ring is removed (Day 7, Visit 2/5 depending on study group), the participant will be asked to rate her level of agreement with the statement "the ring was easy to use by following the provided instructions" on a scale of -4 to 4 (see section 5.4.6). Claim 2 will be validated if the lower bound of the two-sided 95% confidence interval of the proportion of the study population that recorded favorable responses (participants recording a Score of 1, 2, 3 or 4) is greater than or equal to 0.80. The 95% confidence interval will be calculated using the exact test.

Claim 3: VR101 is comfortable during use.

In each daily diary, the participant will be asked to rate her level of agreement with the statement "the ring was comfortable to me today" on a scale of -4 to 4 (see section 5.4.6). Claim 3 will be validated if the lower bound of the 95% confidence interval of the proportion of the study population that recorded favorable responses (participants recording a Score of 1, 2, 3 or 4) is greater than or equal to 0.80. The 95% confidence interval will be calculated using the exact test.

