5.2 Investigational and Predicate Devices

5.2.1 Exposure to VR101 and the sham control

Participants will use VR101 for up to 17 weeks total and the sham control for 4 weeks as described above. Participants will use VR101 for approximately 13 total weeks, consecutively, to evaluate device safety.

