4. Participants will undergo a brief vaginal health assessment which will include a pH test and assignment of VHI scores (see Table 6). During Visit 1, if a participant is assigned a VHI score of 22 or lower (and met all other inclusion/exclusion criteria), she will be enrolled in the study and randomized. The participant will be assigned the next available (lowest remaining) Participant Number.
5. Enrolled participants will be provided with a package of either at least 6 each VR101 devices or at least 6 each sham controls (one for each of the first 4 weeks and at least 2 spares) with printed instructions for use. During Visit 1, the Participant will be given a package containing the Participant Number followed by the letter "A" (for example Participant 1 will be given a package labeled "1A"). During Visit 4, the Participant will be given a package containing the Participant Number followed by the letter "B" (for example Participant 1 will be given a package labeled "1B"). Participant numbers will be pre-randomized by the Sponsor, and only the Sponsor will have access to the randomization schedule. No additional information, verbal or otherwise, will be provided by the clinician to participants on the use of the device.
6. Enrolled participants will be shown to a private clinic area or restroom to self-insert one of the devices from package "A" (Visit 1) or "B" (Visit 4).
7. After insertion, participants will be asked to complete a Post-Insertion Survey that queries their first impressions of the IVR and the insertion process. If a participant has difficulty with placement, she can choose to not place the ring and will be withdrawn from the study. The first ring will remain in the vagina for 7 ± 2 days.
8. Participants will be given a daily diary to complete and return to study staff at each subsequent study visit. The diary will request information on comfort of device use during daily activities and symptoms of vaginal dryness.

J3 Bioscience, Inc.	Clinical Investigation Plan and Protocol CI02	CI02-CIP Rev. 08 Page 39 of 75
	A Pivotal Clinical Investigation to Evaluate the Safety and Efficacy of J3 Bioscience Lubricating Intravaginal Ring VR101 in Relieving Symptoms of Vaginal Dryness	

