5.6 Labeling

Device labeling is provided below for VR101 devices. VR101 labels will include the wording "for investigational use only" and other wording and markings to assure compliance with FDA and ISO 14155 requirements, as appropriate.

Each VR101 device is individually sealed in a polyethylene-lined foil pouch and labeled with CI02-LBL01 Device Label and Identifier. The sealed pouch is then placed in a polyolefin zip-lock bag and the insertion instructions are adhered to the outside of the zip-lock bag. Clinical staff (other than the physician assessing VHI scores) may distribute the bags containing the VR101 packaged devices in sealed pouches to study participants. The draft label and draft instructions for use are shown below.

Instructions for use and labeling of sham rings will be identical to those provided for VR101 devices. As described above, bundles of 6 each VR101 devices or sham controls will be given to participants at the beginning of the crossover study. Only the Sponsor or his or her authorized representative will have knowledge of which packaging identifiers correspond to either VR101 or the sham control. The identity of administered rings will not be disclosed to any clinicians who collect patient or ring (VR101 or sham) data.

Investigational VR101 Label (LBL 001 R00)

VR101 Vaginal Lubrication Ring

*Manufactured by: J3 Bioscience, Inc.,
[name]*

VR101 is a personal lubrication device for vaginal application intended to moisturize and lubricate, to enhance the ease and comfort of intimate sexual activity, and supplement the body's natural lubrication.

CAUTION: Investigational device limited to investigational use only.

CONTRAINdications: Use is restricted to patients enrolled in VR101 Clinical Study.

WARNINGS: For vaginal use only. VR101 is not a contraceptive, does not contain a spermicide and does not protect from any sexually-transmitted infections. Keep out of reach of children. Do not ingest or place in mouth. If vaginal irritation occurs, discontinue use. If symptoms persist, contact your clinician. If pregnant or breast feeding, consult your healthcare provider before use.

Store at room temperature. LBL 001 R00 2017-03

Expiration Date:

SEE INSTRUCTIONS FOR USE

Investigational VR101 Instructions for Use (LBL 002 R00)

VR101 Insertion Instructions

Prior to use, inspect each package for damage.

Do not use if package or device appears damaged.

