8.12 Definition of Study Populations for Analysis

THE FOLLOWING STUDY POPULATIONS HAVE BEEN DEFINED FOR THIS INVESTIGATION:

Intent-to-Treat (ITT) Primary Efficacy Hypothesis Population: All patients who meet inclusion/exclusion criteria and are randomized will be included. Any missing day 0 or day 28 VHI scores will be imputed as defined in section 8.8.

J3 Bioscience, Inc.	Clinical Investigation Plan and Protocol CI02	CI02-CIP Rev. 08 Page 57 of 75
	A Pivotal Clinical Investigation to Evaluate the Safety and Efficacy of J3 Bioscience Lubricating Intravaginal Ring VR101 in Relieving Symptoms of Vaginal Dryness	

Menopausal Population: All members of the ITT population who self-report to being menopausal (have not experienced a menstrual period in the 12-month period prior to the study).

Safety Population: All VR101 devices in all study arms that are successfully inserted and used in accordance with the provided instructions for use will be included as a basis for determination of SADE proportion.

Claim 1 Population: All participants who report a daily vaginal dryness severity following their first VR101 use (Visit 2/5, depending on study arm) and report a weekly average vaginal dryness severity prior to their first VR101 insertion (Visit 1/4, depending on study arm), will be included in the analysis for Claim 1. See section 5.4.5 for relevant survey questions.

Claim 2 Population: All participants in group V1S2 who respond to the appropriate survey question (see section 5.4.6) immediately following their first VR101 insertion (Visit 1) will be included in the analysis for Claim 2.

Claim 3 Population: All daily diary responses recorded regarding VR101 comfort during use (see section 5.4.6) will be included in the analysis for Claim 3.

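### Claim 3 (comfort) is counted in recorded diary days in section 8.12 and in participants in section 4.2.3; neither says how a woman who stops VR101 is counted, and counting days favours the claim if uncomfortable women stop early

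*Combined protocol and SAP*

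**What the plan says.** Section 8.12 defines the Claim 3 population as diary entries: "All daily diary responses recorded regarding VR101 comfort during use (see section 5.4.6) will be included in the analysis for Claim 3". A day with no entry is not in the denominator.

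Section 4.2.3 states the pass rule: "Claim 3 will be validated if the lower bound of the 95% confidence interval of the proportion of the study population that recorded favorable responses", explained in brackets as "participants recording a Score of 1, 2, 3 or 4", "is greater than or equal to 0.80", with an exact interval. The section gives no rule for turning a woman's many diary days into one result.

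Neither section says what happens to a woman who stops VR101. Imputation in section 8.8 covers only data that bear on the primary efficacy hypothesis.

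Three other places matter:
- The label in section 5.6 says "If vaginal irritation occurs, discontinue use".
- The Visit 1/4 steps in section 5.4.3 say "If a participant has difficulty with placement, she can choose to not place the ring and will be withdrawn from the study".
- Section 5.2.1 says "Participants will use VR101 for up to 17 weeks total", so a woman who continues can record many more days than one who stops.

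Claim 3 is last in the testing hierarchy (section 8.11), and section 8.5 says that the claims do not affect the success or failure of the investigation.

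**The concern.** The labelling claim will be read as a statement about women: that women find VR101 comfortable. The only defined analysis set counts days. A woman's weight is then the number of days on which she made an entry, and discomfort is one plausible reason for making few. The label gives such a woman a direct route out of the data, and a woman who cannot place the ring may leave no VR101 diary day at all.

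If discomfort leads to early stopping, the proportion moves toward the claim. This is a different matter from the exact interval treating repeated days from one woman as independent. Widening the interval for repeated ratings leaves the point estimate where it is.

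**Working it through.** **Inputs from the documents.** 72 women enrolled (section 5.3.6). 11 withdrew during the 11-week crossover (section 8.4). Four 7-day VR101 rings in the crossover, so 28 VR101 days (section 5.1). Limit 0.80, exact interval (section 4.2.3). The interval is taken as two-sided: Claim 2 says so, Claim 3 does not say.

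**Assumptions.** Which women stop, on which day and why; the favourable rate among the others; that all 72 women inserted VR101; complete diaries up to stopping. Each woman who stops scores every recorded day unfavourable.

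**The plan's own figure.** The documents give no sample size or power for Claim 3. The stated withdrawal rate reproduces: 11/72/11 = 1.39% per week, and the exact 95% interval for 11/792 is 0.70% to 2.47%, as in section 8.4.

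**Scenario A: 18 of 72 women (25%) stop after day 7.** The other 54 record 54 × 28 = 1512 days and the 18 record 18 × 7 = 126, total 1638. A quarter of the women supply 126/1638 = 7.7% of the days. Let f be the others' favourable rate; the day-level proportion is 1512f/1638.

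| f | Favourable days | Proportion | Exact lower limit | Result |
|---|---|---|---|---|
| 95% | 1436/1638 | 87.7% | 86.0% | pass |
| 90% | 1361/1638 | 83.1% | 81.2% | pass |
| 85% | 1285/1638 | 78.4% | 76.4% | fail |

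By woman: 54/72 = 75.0%, lower limit 63.4%, fail in every row.

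**Scenario B: the same 18 women stay for all 28 days.** Others always favourable: 1512/(72 × 28) = 1512/2016 = 75.0%, lower limit 73.0%, fail. The day-level pass in A therefore comes from early stopping.

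**Scenario C: only the 11 observed withdrawals, all assumed to be for VR101 discomfort at day 3, others always favourable.** By day: 61 × 28 = 1708 favourable of 1708 + 33 = 1741, 98.1%, lower limit 97.3%, pass. By woman: 61/72 = 84.7%, lower limit 74.3%, fail.

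**Scenario D: 18 uncomfortable women, of whom 11 stop at day 3 and 7 stay 28 days.** Total 1512 + 33 + 196 = 1741. With the other 54 favourable on 100%, 95% or 90% of days, the lower limits are 85.2% (pass), 80.6% (pass) and 76.2% (fail). By woman it is again 54/72, fail.

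**What a per-woman pass needs.** 64/72 has lower limit 79.3% and 65/72 has 81.0%, so at least 65 of 72 women must be favourable.

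**The case against.** **The pass rule already names participants.** It does, and a reader could say that 4.2.3 governs. But it has no per-woman summary and no rule for women who stop, while 8.12 expressly puts every diary response in the analysis. The conflict has to be resolved in writing.

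**Days of use is a defensible target for a claim about comfort during use.** This stands in part. If that is the target, the plan should say so, and the claim should not be expressed as a proportion of the study population.

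**A quarter of women stopping is more than was seen.** Correct: 11/72 = 15.3% withdrew in the crossover for any reason, some possibly during sham use or washout. The documents do not attribute any withdrawal to discomfort, and all 21 pilot women completed (section 2.4). Scenarios C and D stay within 11 withdrawals, but still assume the reason and the timing.

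**Stronger readings that the documents do not support.** A reader might infer that the claim would pass even if the interval were widened to one effective response per woman. That needs long diaries and a high favourable rate. Take the 61 women left after the crossover, 25% stopping at day 7, and others favourable on 95% of 105 days (the mean of 13 × 7 = 91 and 17 × 7 = 119). The pooled value is 92.9%, about 57/61, lower limit 84.1%. With 28-day diaries it is 87.7%, about 53/61, lower limit 75.8%, fail. With 105 days and 90% favourable it is 88.0%, about 54/61, lower limit 77.8%, fail. The 105 days are not established: Tables 4 and 5 mark no diary collection after Visit 6, and section 5.3.5 has V1S2 women stop VR101 when the blind is broken. Nor can women who completed the crossover have stopped VR101 for good at day 7, so 61 is the wrong base.

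A reader might also assume that reasons for stopping are already on record. Section 14 lets women leave without giving one, and section 5.3.5 asks the diary only for dates and times of removal.

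**Conclusion.** The concern holds in conditional form. Sections 4.2.3 and 8.12 disagree on the unit of Claim 3, and no text covers women who stop. Followed as written, 8.12 weights women by recorded days, which favours the claim if women who find the ring uncomfortable stop early. Under the plan's day-level rule that can reverse the result: in scenario A with f = 95%, a lower limit of 86.0% by day against 63.4% by woman.

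The size rests on assumed stopping days, reasons and favourable rates, and the reversal is not general: the day-level result also fails when the others are favourable on 85% of days and stopping is at day 7, or when uncomfortable women keep recording for 28 days. The documents do not show that a quarter of women found VR101 uncomfortable, or that the bias has occurred. Because Claim 3 does not affect trial success, this should be corrected but does not threaten the primary conclusions.

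**What to change.** Align section 8.12 with section 4.2.3:

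- **Unit and denominator:** one outcome for each woman who inserted at least one VR101.
- **Window:** fixed, for example her first 28 VR101 days.
- **Favourable:** most of her rated days in the window score 1 to 4.
- **Unfavourable:** also any woman who stopped VR101 in the window for discomfort or a ring-related reason.
- **No recorded reason:** a stated rule, for example count as unfavourable, with a sensitivity analysis.
- **Could not place the ring:** report separately or in a sensitivity analysis, since this bears on ease of use (Claim 2) as much as on comfort.
- **Test:** exact interval, stated as two-sided, and the 0.80 limit applied to women. Report pooled diary days descriptively.

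The window and the majority rule are choices; others would serve if fixed before the data are examined. No new visit or measurement is needed, though reasons for stopping must be sought where they are given.

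The costs are a less favourable proportion, a wider interval and a harder pass (65 of 72 if all 72 women inserted VR101), and Sponsor and IRB approval, which section 10 requires for a change to data analysis.

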9 DATA COLLECTION AND MANAGEMENT

Paper CRFs (Case Report Forms) will be used for data collection during the study. Paper CRFs will be printed on 2-part NCR (no carbon required) with a copy retained by the investigators at the conclusion of the study.

Data from CRFs will be transcribed into an electronic database by the sponsor using double data-entry following study opening. Since the hand-written original CRF copies will serve as the official study record, Sponsor/analyst bias does not present concern to the study, provided double data-entry and an additional, independent data audit of database transfer is performed.

Following the final participant's Visit 6, data from the comparative efficacy (crossover) study (all data from Visits 1-5 and all data from Visit 6 except for the Post-Insertion survey) can be locked and the study blind can be broken. At this time, comparative efficacy (crossover) study data will be available for analysis.

10 AMENDMENTS TO THE CIP

Amendments to the CIP require written authorization of the Sponsor before they are recommended to the IRB(s) for approval. No changes will be made to the devices or the CIP without Sponsor and IRB approval.

J3 Bioscience, Inc.	Clinical Investigation Plan and Protocol CI02	CI02-CIP Rev. 08 Page 58 of 75
	A Pivotal Clinical Investigation to Evaluate the Safety and Efficacy of J3 Bioscience Lubricating Intravaginal Ring VR101 in Relieving Symptoms of Vaginal Dryness	

To revise the CIP, the written proposed changes will be reviewed and approved by the Sponsor and submitted to the IRB for approval before any changes to the device, treatment procedures, assessment methods, data analysis, or any other procedures documented in the CIP may be made, or any additional information may be added.

11 DEVIATIONS FROM THE CIP

11.1 Acceptable Circumstances for Deviations to the CIP

Investigators shall not deviate from this CIP, except under the following circumstances:

- Deviations may be made with prior approval of the Sponsor if made in deference to participant's rights, safety and well-being, or the scientific integrity of the clinical investigation.
- Under emergency circumstances, deviations from the CIP to protect the rights, safety and well-being of human participants may proceed without prior approval of the Sponsor and the IRB.

Such deviations shall be documented and reported to the Sponsor and the IRB as soon as possible.

11.2 Procedure for Disqualification and Replacement of a Principal Investigator

Any PI (Principal Investigator) or Sub-PI who has been documented to consistently deviate from this CIP, and/or consistently endanger participant's rights, safety and wellbeing, or the scientific integrity of the clinical investigation, may be removed from the investigation.

12 DEVICE ACCOUNTABILITY

12.1 Access to Devices

Investigational rings (VR101 devices and sham rings) will be stored in a locked cabinet that will only be accessible by the PI and study coordinator. Only the study coordinator and designated staff members will have access to this cabinet and to the Device Accountability log, which contains the list of device numbers assigned to each subject.

12.2 Physical Location of Investigational Devices

The Sponsor shall keep records to document the physical location of all investigational devices from shipment of investigational devices and shams to the investigation sites until return or disposal.

12.3 Use of Devices

Investigational devices and sham rings shall only be used in a manner specified by this CIP and the clinical protocol.

J3 Bioscience, Inc.	Clinical Investigation Plan and Protocol CI02	CI02-CIP Rev. 08 Page 59 of 75
	A Pivotal Clinical Investigation to Evaluate the Safety and Efficacy of J3 Bioscience Lubricating Intravaginal Ring VR101 in Relieving Symptoms of Vaginal Dryness	

12.4 Distribution of Devices from the Sponsor to Clinical Sites

The Sponsor will deliver a specified number of VR101 and sham samples to each clinical site.

Each clinical site will maintain Device Accountability Logs (see below), to which an entry must be made each time a VR101 or sham ring is given to a participant, or unused spare or used VR101 or sham ring is returned to the clinic by a participant.

12.5 Device Accountability Log

The principal investigator, study coordinator or an authorized designee shall keep a Device Accountability Log for VR101 and sham control rings which shall include:

- The date of receipt and number of devices received from the Sponsor.
- The lot number or any other unique identifier of the rings received.
- The expiration date of rings received, if applicable.
- The number and unique IDs of rings administered to each participant, along with their unique participant identifier, and the date issued.
- The number of unused rings returned by each participant, along with their unique participant identifier, device identifiers and the date.
- The number of used rings received from each participant along with their unique participant identifier, device identifiers and the date.

13 ADVERSE EVENTS, ADVERSE DEVICE EFFECTS AND DEVICE DEFICIENCIES AND REPORTING EVENTS AND DEFICIENCIES

All Adverse Events reported by participants or observed by a clinician during the study, whether or not Device Related, must be recorded using the Adverse Event Form (Attached). All Adverse Event Forms must be provided to the Sponsor. Certain Adverse Events must be reported to the Sponsor, IRB and/or FDA as they occur throughout the study (see below and in Sections 13.7 through 13.11).

SAEs and SADEs (as defined below) are to be reported to the Sponsor and IRB within 24 hours of the PI becoming aware of their occurrence.

All ADEs (as defined below) are to be reported to the Sponsor within 5 days of their occurrence if study staff determines that they are possibly, probably or definitely related to use of an investigational device (VR101 or sham control).

13.1 Definitions

Definitions below were constructed based on guidance from and definitions provided in ISO 14155 and 21 CFR 812.3.

J3 Bioscience, Inc.	Clinical Investigation Plan and Protocol CI02	CI02-CIP Rev. 08 Page 60 of 75
	A Pivotal Clinical Investigation to Evaluate the Safety and Efficacy of J3 Bioscience Lubricating Intravaginal Ring VR101 in Relieving Symptoms of Vaginal Dryness	

Adverse Event (AE): Any untoward medical occurrence, unintended disease or injury, or untoward clinical signs (including abnormal laboratory findings) in subjects, users or other persons, whether or not related to VR101 use.

Serious Adverse Event (SAE): An AE that leads to:

- Death
- A serious deterioration in the health of the participant, that resulted in any of the following:
 - A life-threatening illness or injury
 - A permanent impairment of a body structure or a body function
 - In-patient or prolonged hospitalization
 - Medical or surgical intervention to prevent life-threatening illness or injury or permanent impairment to a body structure or a body function
- Fetal distress, fetal death or a congenital abnormality or birth defect.

Adverse Device Effect (ADE): An AE related to use of VR101.

Serious Adverse Device Effect (SADE): An ADE that results in any of the consequences characteristic of a SAE.

Unanticipated Serious Adverse Device Effects (USADE): Any SADE that was not previously identified in nature, severity, or degree of incidence in this CIP or application (including a supplementary plan or application), or any other unanticipated serious problem associated with a device that relates to the rights, safety, or welfare of subjects.

Use Error: Act or omission of an act that results in a different response to VR101 than intended or than expected by the user.

Device Deficiency: Inadequacy of a medical device (VR101) with respect to its identity, quality, durability, reliability, safety or performance.

The following table, copied from ISO 14155:2011, summarizes how adverse events will be categorized.

J3 Bioscience, Inc.	Clinical Investigation Plan and Protocol CI02	CI02-CIP Rev. 08 Page 61 of 75
	A Pivotal Clinical Investigation to Evaluate the Safety and Efficacy of J3 Bioscience Lubricating Intravaginal Ring VR101 in Relieving Symptoms of Vaginal Dryness	

Adverse event categorization

Table F.1 presents categories of adverse events.

Table F.1 — Categories of adverse events

ADVERSE EVENTS	Non-device-related	Device- or procedure-related	
Non-serious	Adverse Event (AE) ^a (3.2)	Adverse Device Effect (ADE) (3.1)	
Serious	Serious Adverse Event (SAE) ^b (3.37)	Serious Adverse Device Effect (SADE) (3.36)	
		Anticipated	Unanticipated
		Anticipated Serious Adverse Device Effect (ASADE) (3.42, Note)	Unanticipated Serious Adverse Device Effect (USADE) (3.42)

^a Includes all categories.
^b Includes all categories that are serious.

